# Protocol Details

## Basic Info

Confirmation Number: **djabjdjj**  
Protocol Number: **832891**  
Created By: **[name]**  
Principal Investigator: **[name]**  
Protocol Title: **Optimizing Neuromodulation through Individualized Stimulation Frequencies**  
Short Title: **Individualized Loop TMS**  
Protocol Description: Transcranial Magnetic Stimulation (TMS) is a non-invasive mechanism for stimulating the human brain. TMS can potentiate or inhibit activity in various brain regions, and it allows researchers to exert causal control over neural pathways. We will use real-time fMRI brain readout to optimize TMS delivery and measure changes in behavioral and brain response following the neuromodulation in healthy participants.  
Submission Type: **Biomedical Research**  
Application Type: **EXPEDITED Category 1**

**Responsible Org (Department/School/Division):**

10579 - PS-Center for the Neuroscience of Depression & Stress

#### **Disclosure of Significant Financial Interests\***

Does any person who is responsible for the design, conduct, or reporting of this research protocol have a **FINANCIAL INTEREST**?

No

#### **Penn Intellectual Property\***

To the best of the Principal Investigator's knowledge, does this protocol involve the testing, development or evaluation of a drug, device, product, or other type of intellectual property (IP) that is owned by or assigned to the University of Pennsylvania?

No

#### **Certification**

I have reviewed the *Financial Disclosure and Presumptively Prohibited Conflicts for Faculty Participating in Clinical Trials* and the *Financial Disclosure Policy for Research and Sponsored Projects* with all persons who are responsible for the design, conduct, or reporting of this research; and all required Disclosures have been attached to this application.

Yes

## **Biomedical Research**

#### **Clinical Trial\***

Is this a clinical trial? Please note the following definition: Clinical trial is defined as a research study in which one or more human subjects are prospectively assigned to one or more interventions (which may include placebo or other control) to evaluate the effects of the interventions on biomedical or behavioral health-related outcomes. See CFR 45.46.102(b)

Yes

If Yes, please be aware that for each clinical trial conducted or supported by a Federal department or agency, one IRB-approved informed consent form used to enroll subjects must be posted by the awardee or the Federal department or agency component conducting the trial on a publicly available Federal Web site that will be established as a repository for such informed consent forms. For more guidance, please see: <https://irb.upenn.edu/homepage/how-to-submit/initial-submission/2018-common- rule>. Please see: <https://irb.upenn.edu/clinicaltrials> for additional clinical trial requirements.

#### **Investigator Initiated Trial\***

Is this an investigator initiated trial? Please select "Yes" if ALL the following conditions are met: The research is subject to FDA regulations for human subjects research. The individual PI both initiates (plans and designs) and conducts an investigation and under whose immediate direction the investigational agent is administered or dispensed. The individual investigator has absolute responsibility and accountability and designs, conducts, monitors, manages the data, prepares reports and oversees all regulatory and ethical matters. See 21 CFR 312.3

Yes

If Yes, please be aware that the investigator may be required to create and manage a record of this trial in <https://clinicaltrials.gov>.

#### **Drugs or Devices\***

Does this research study involve Drugs or Devices?

Yes: Investigational devices that may qualify as Non-Significant Risk.

#### **IND Exemption**

**For studies that fall under an IND exemption, please provide the number below**

**For studies including IND or IDE's, please provide the number(s) below**

#### **IDE Review\***

NOTE: For research involving investigational devices, you are required to review the guidance on Managing Research Device Inventory. Consult the Penn Manual for Clinical Research: [https://www.med.upenn.edu/pennmanual/secure/investigational-product-management-at-sites-not-using-investigational-drug-services-\(ids\).html](https://www.med.upenn.edu/pennmanual/secure/investigational-product-management-at-sites-not-using-investigational-drug-services-(ids).html) Please check the box Yes if you have reviewed the guidance.

Yes

#### **Research Device Management\***

Please indicate how research device(s) will be managed.

The device receipt, storage and dispensing is being conducted by the research team (please provide information in the protocol summary as to how this will be conducted)

#### **Drug, Herbal Product or Other Chemical Element Management \***

Please indicate how drugs, herbal products or other chemical entities will be managed.

Not Applicable (no drugs, herbal products or other chemical entities)

#### **Radiation Exposure\***

Are research subjects receiving any radiation exposure solely because they are enrolled in this protocol? (e.g. X-rays, CT, Fluoroscopy, DEXA, pQCT, FDG, Tc-99m, etc.)? IF YES, the protocol must be approved by the RRSC (Radiation Research Safety Committee). Consult EHRS web site: [www.ehrs.upenn.edu/protocols/radiohuman.html](http://www.ehrs.upenn.edu/protocols/radiohuman.html) for more information. If you have questions, email [[contact]](mailto:[contact]) or [[contact]](mailto:[contact]) If your protocol includes Nuclear Medicine Procedures, the protocol must be reviewed by the Nuclear Med Operations Committee: <https://redcap.link/NMOPS>

No

#### **Gene Transfer\***

Does this research involve gene transfer (including all vectors) to human subjects? IF YES, the protocol must be approved by the Institutional Biosafety Committee. Consult EHRS web site: [www.ehrs.upenn.edu/protocols/bio\\_humans.html](http://www.ehrs.upenn.edu/protocols/bio_humans.html) for submission requirements. If you have questions, call [contact]. The protocol may also require review by the Senior Vice Provost for Research's Human Research Advisory Committee(HRAC). The IRB will notify the PI and study staff if this review is warranted.

No

#### **Human Source Material\***

Does this research include collection or use of human source material (i.e., human blood, blood products, tissues or body fluids)? IF YES, consult the EHRS web site: [www.ehrs.upenn.edu/programs/bio/bbpathogens.html](http://www.ehrs.upenn.edu/programs/bio/bbpathogens.html) for information on OSHA Bloodborne Pathogens requirements (training, vaccination, work practices and Exposure Control Plan). If you have questions, call [contact].

No

#### **Image Guided Biopsies\***

Does the research involve imaging guided biopsy? IF YES, please contact the Clinical Imaging Core. See <https://www.med.upenn.edu/cbi> for more details. Any questions should be directed to the Director of Research Operations, Dept of Radiology, [name].

No

**Computerized Tomography (CT) Studies\***

Does the protocol involve CT scans that are not considered standard of care and are being performed for research purposes? IF YES, complete the CACTIS Committee Application: <https://is.gd/CACTIS> and consult CACTIS website: <http://www.uphs.upenn.edu/radiology/research/labs/cactis/> for application requirements.

No

**CAMRIS and MRI Studies\***

Is an MRI scan being performed for research only and NOT considered standard of care (example: specific scanner, parameters or solely for the purposes of research)? NOTE: Research/non-standard use of MRI may include but is not limited to any of the following: Situations in which MRI results may impact subjects current clinical care plan or treatment decisions, such as: The study requires a customized report with specifics regarding the study protocol (i.e., specific measurements or details); Introduction of a device of any kind during the MRI that is not used during a 'standard of care' type scan. Your MRI is not consistent with standard care time points for MRI imaging. Your MRI is not paid for by insurance. IF YES, consult CAMRIS website: <https://www.med.upenn.edu/camris/application-and-faq.html> for application requirements and required institutional consent form language.

Yes

**Investigational Agent or Device within the Operating Room\***

Does the research project involve the use of an investigational agent or device within the Operating Room?

No

**Cancer Related research not being conducted by an NCI cooperative group\***

Does this protocol involve cancer-related studies in any of the following categories? Therapeutic, Prevention, Supportive Care, Screening, Early Detection, or Diagnostic, Epidemiologic, Observational, Outcome, Ancillary or Correlative. For a description of these categories, see [http://www.ctsrmc.org/submitting\\_a\\_protocol.php](http://www.ctsrmc.org/submitting_a_protocol.php) NCI Cooperative Groups are as follows: Alliance for Clinical Trials in Oncology NCI Clinical Trials Group (Canadian Cancer Society) (NCCTG) Children's Oncology Group (COG) NRG Oncology Group ECOG-ACRIN Cancer Research Group Southwest Oncology Group (SWOG) IF YES, the protocol must be submitted to the Cancer Center's Clinical Trials Scientific Review Committee for scientific review and approval prior to obtaining IRB approval. Consult the CTSRM website: [www.ctsrmc.org](http://www.ctsrmc.org) for application requirements

No

**Processing of Materials\***

Will the research involve processing (such as over encapsulating, or compounding)?

No

**In-House Manufacturing of Materials\***

Will the research involve processing (such as over encapsulating, or compounding)?

No

**HIPAA / Protected Health Information**

Does the research proposal involve accessing (viewing / using), collecting, or disclosing of protected health information (PHI) directly from participants or their medical or dental record for research purposes? Yes

**Indicate which item is provided with this submission:**

Modified research informed consent document that incorporates HIPAA requirements

**Cohort/data analysis tools used****Remote Study Visits**

Does the research proposal involve conducting research visits remotely via any type of video conferencing software?

Yes

**Conference software used**

Zoom

**CHPS Resources\***

Does the research involve CHPS resources?

No

**HUP Inpatient Nursing Resources**

Does this research include an inpatient admission at HUP?

No

**Pathology and Laboratory Medicine Resources\***

Will samples be collected by hospital phlebotomy and/or processed or analyzed by any of the clinical laboratories of the University of Pennsylvania Health System?

No

**Research Involves Apheresis, Cell Collection, and/or Blood Product Collection\***

Does this research involve collection of blood products in the Penn Donor Center and/or the use of apheresis for treatment or collection of cells or other blood components?

No

**Research involving blood transfusion or drug infusions\***

Will your research involve blood transfusion or infusion of study drug in 3 Ravdin Apheresis Unit for research purposes?

No

**Trial in Radiation Oncology**

Is this research a prospective trial being done in Radiation Oncology, and if so, has this protocol been approved by the Radiation Oncology Protocol committee?

N/A

**Study in Radiation Oncology**

Is this research a retrospective study being done in Radiation Oncology, and if so, has this project been reviewed by the Radiation Oncology Clinical Research Group?

N/A

**Use of UPHS services\***

Does your study require the use of University of Pennsylvania Health System (UPHS) services, tests or procedures , whether considered routine care or strictly for research purposes? (UPHS includes all Penn hospitals and clinical practices, including the Clinical Care Associates network of community practices). Examples of UPHS services/tests/procedures includes the Clinical Translational Research Center (CTRC), laboratory tests, use of the pathology lab, cardiovascular imaging tests or radiology imaging tests (whether being billed via the Service Center or through UPHS), other diagnostic tests & procedures and associated professional services, etc.

No

**Veteran's Affairs (VA) Patients or Subjects**

Does your study involve data from Veteran's Affairs (VA) patients or subjects?

No

**If yes, was this approved by the Philadelphia VA?**

No

**Out of State Research**

Will any Penn personnel conduct any research activities outside of the State of Pennsylvania?

No

**Research involving Virtua Health**

Will any Penn personnel conduct any research activities at a Virtua Health site location, OR in collaboration with Virtua Health System personnel, OR using any Virtua Health System resources (e.g.,

medical records)?

No

**Primary Focus\***

Other

**Protocol Interventions**

Sociobehavioral (i.e. cognitive or behavioral therapy)

Drug

Device - therapeutic

Device - diagnostic (assessing a device for sensitivity or specificity in disease diagnosis)

Surgical

Diagnostic test/procedure (research-related diagnostic test or procedure)

Obtaining human tissue for basic research or biospecimen bank

Survey instrument

None of the above

The following documents are currently attached to this item:

*There are no documents attached for this item.*

**Department budget code**

000 - 000 - 0 - 000000 - 0000 - 0000 - 0000

**Funding Sponsors**

**Funding sponsors billing address**

If you have selected a commercial or industry sponsor, please provide the appropriate address and contact information for the Sponsor for the purposes of billing for IRB review fees (initial review, continuing review and convened modification fees apply here). If the Sponsor is not industry/ commercial, this information is not necessary to provide with your application.

**Funding sponsors gift**

Is this research being funded by a philanthropic gift?

**Regulatory Sponsor**

**IND Sponsor**

none

000 - 000 - 0 - 000000 - 0000 - 0000 - 0000

### **Industry Sponsor**

None

#### **Project Funding\***

Is this project funded by or associated with a grant or contract?

Yes

### **Selected Proposals**

Proposal No	Title
10070605	Individualized Closed Loop TMS for Working Memory Enhancement

#### **Sponsor Funding**

Is this study funded by an industry sponsor?

No

#### **Status of contract**

**The following documents are currently attached to this item:**

*There are no documents attached for this item.*

## **Multi-Center Research**

#### **Penn as lead**

1. Is this a multi-center study where Penn is serving as the Lead Site or the Penn PI is serving as the Lead Investigator?

No

#### **Management of Information for Multi-Center Research**

#### **Penn irb of record**

2. Is this a multi-center study where the Penn IRB will be asked to serve as the IRB of Record for other external study sites?

No

#### **Other Sites**

No other sites

## **Protocol**

#### **Abstract**

Transcranial magnetic stimulation (TMS) is a non-invasive mechanism for stimulating brain regions in humans. TMS can potentiate or inhibit activity in various brain regions, and it allows researchers to exert causal control to explore and define network connectivity among brain regions. Using real-time brain readouts combined with interleaved TMS/fMRI, we will compare the optimal and the least optimal stimulation frequency based on individualized functional connectivity networks. By comparing brain and behavioral changes after three days of neuromodulation at optimal and least optimal

stimulation frequency, we aim to explore whether optimal stimulation frequency will lead to more robust brain and behavior responses to repetitive TMS (rTMS).

## **Objectives**

### **Overall objectives**

We aim to evaluate whether optimized frequency (compared to the least-optimized frequency) of excitatory TMS will generate better results in behavior and brain activity among healthy participants. Specifically, we will develop a novel tool to compute individualized multi-scale functional connectivity networks using data from baseline resting and task-evoked brain states. Building on that, we will utilize recurrent neural networks (RNN) with long short-term memory (LSTM), a promising deep learning technique, to generate brain decoding models and obtain real-time readouts of brain states. We will then establish a closed loop of rTMS and brain readouts, fine-tuning the rTMS frequency to determine the optimal stimulation frequency for each participant. Participants will receive their optimal stimulation frequency of rTMS over a three-day neuromodulation session and their least optimal stimulation frequency (the frequency least successful in moving their brain state) over another three-day neuromodulation session (order counterbalanced across subjects). We hypothesize that optimal frequency will drive performance improvements and brain changes more than the least optimal frequency.

### **Primary outcome variable(s)**

Behavior change (task performance) and brain activity change (in-scanner brain readouts during the working memory task or at rest) in response to neuromodulation.

### **Secondary outcome variable(s)**

Correlation between changes in behavioral measures and changes in network connectivity before and after the neuromodulation.

### **Background**

Repetitive TMS (rTMS) has been widely adopted to non-invasively stimulate the brain to improve working memory (WM) performance in both clinical and non-clinical samples (Brunoni & Vanderhasselt, 2014). However, behavioral and symptom responses to TMS remain heterogeneous and the factors governing the strength and direction of rTMS effects across individuals remain largely unknown. Accumulating evidence has demonstrated that TMS efficacy hinges upon the precision of TMS targeting, and individualized functional connectivity networks (FCNs) may help accurately identify TMS targets for individuals (Fox, Buckner, White, Greicius, & Pascual-Leone, 2012; Fox, Liu, & Pascual-Leone, 2013; Weigand et al., 2018) since effects of stimulation are propagated throughout both local and distributed brain networks (Herbsman et al., 2009; Kloppel et al., 2008). The functional brain state varies across individuals and within individuals over time (Bassett, Wymbs, Porter, Mucha, Carlson, & Grafton, 2011; Calhoun, Miller, Pearson, & Adal, 2014; Finn, Scheinost, Finn, Shen, Papademetris, & Constable, 2017), which could substantially alter the impact of TMS. Preliminary research suggests that manipulating brain states during the delivery of repetitive TMS (rTMS) neuromodulation augments the behavioral impact of rTMS (Luber et al., 2017). Through manipulation of brain state with a related behavioral task and using fMRI as the feedback signal, it may be possible to tune rTMS delivery to maximally impact the desired brain states in awake behaving study participants in a highly individualized manner. Therefore, improved efficacy of TMS could be achieved through precise TMS targeting and optimal TMS delivery tailored for individuals and optimized online based on real-time readouts of brain states. FCNs derived from functional MRI have demonstrated promising performance for identification of reproducible individualized targets. However, existing methods are limited in that they typically identify group-level functional connectivity networks (FCNs) and focus on resting state fMRI alone. Our recent work suggests that individualized, sparse, non-negative FCNs provide enhanced ability for characterizing the functional brain of individual subjects (Li, Satterthwaite, & Fan, 2017). Moreover, recent evidence suggests that task fMRI can improve upon within-subject and between-subject estimates of stable brain network representations as compared with resting state fMRI only (Finn, Scheinost, Finn, Shen, Papademetris, & Constable, 2017). Based on these findings, current study will focus on both resting and task-evoked brain states and individualized, multiscale, hierarchical functional neuroanatomy, and we will extend upon our recent published work (Li et al., 2017, 2016; Li, Zhu, & Fan, 2018) using deep matrix decomposition techniques (Trigeorgis, Bousmalis, Zafeiriou, & Schuller, 2014; Zhao, Ding, & Fu, 2017). This strategy will yield a set of individualized FCNs that share similar spatial patterns across subjects at multiple scales with a hierarchical organization,

facilitating individualized precise TMS targeting. Another major innovation that will facilitate optimal TMS delivery is the brain decoding for real-time online brain readouts. Recent studies have demonstrated promising brain decoding performance of prediction models built upon functional connectivity measures among FCNs within time windows with a fixed width (Shirer, Ryali, Rykhlevskaia, Menon, & Greicius, 2012; Richiardi, Eryilmaz, Schwartz, Vuilleumier, & Van De Ville, 2011). However, such fixed time windows are not likely optimal over different brain states that change at unpredictable intervals. Meanwhile, recurrent neural networks (RNNs) with long short-term memory (LSTM) (Hochreiter & Schmidhuber, 1997) have achieved remarkable advances in sequence modeling (Lipton, Berkowitz, & Elkan, 2015), and these techniques have been successfully applied to EEG and ECoG data analysis (Glaser, Chowdhury, Perich, Miller, & Kording, 2017; Schwemmer et al., 2018). Our recent study has demonstrated that brain decoding models built upon individualized FCNs using LSTM RNNs accurately decode fine-grained WM tasks and motor tasks in real time (Li & Fan, 2018). Therefore, here we will build brain decoding models to obtain real-time readouts of brain states using LSTM RNNs. Besides TMS targeting, rTMS frequency has clear neurobiological consequences successfully measured in-vivo in non-human animal brains in a landmark study (Allen, Pasley, Duong, & Freeman, 2007). Our team has adopted the interleaved TMS/fMRI technique which will allow stimulation of specific nodes while recording fMRI responses from all other brain regions (Chen et al., 2013; Fonzo et al., 2001; Nahas et al., 2001). Building on this basic strategy and the innovative methodology mentioned above, we can fine-tune the TMS frequency based on real-time feedback of TMS induced effects on the brain. Specifically, we will target FCNs identified by a brain decoding model built using LSTM RNNs, apply short trains of in-scanner rTMS, monitor the resulting brain response with fMRI, and tune TMS delivery accordingly. As a result, we can optimize noninvasive brain stimulation through individualized target and frequency. By comparing behavioral and brain responses with optimized and non-optimized stimulation frequencies, this study will provide us novel insight to variability in response to TMS and will potentially enhance the capabilities of the existing device.

## **Study Design**

### **Phase\***

Not applicable

### **Design**

This study will recruit 38 healthy participants, who will be recruited through the community via study advertisements. Prior to any study visits, all subjects will be pre-screened through a phone interview with a trained member of the study team or an online self-report screening, both through REDCap. The study involves 11 study visits. The first study visit will consist of a consenting and extended screening visit. All participants will have the opportunity to ask questions before signing the electronic consent form. We will complete a semi-structured clinical interview and will demonstrate TMS to ensure the participant is comfortable with all study procedures. This visit will be completed both remote and in- person. The second study visit will involve a 1-hour MRI scan. During the scan, the participant will complete multiple computerized tasks. The MRI scan will include both structural and functional scans, and those scans will be used to localize the stimulation target for the subsequent sessions. The third study visit will be a 2-hour TMS/fMRI session, and the participant will engage in behavioral tasks while interleaved rTMS rounds are delivered at different excitatory frequencies (frequency range: 2Hz-20Hz). This scan will be used to determine the optimal stimulation frequency for the individual participant. The fourth, fifth, and sixth study visits will involve neuromodulation with either the optimized frequency or the frequency least successful in moving a participants brain state, as determined from the third study visit. Each subject will receive ~3000 pulses in each session, including the pulses from the motor threshold determination. We will determine the adjusted MT by using the Stokes equation, which accounts for differences in cortical distance from the site relative to motor cortex (where the motor threshold is found). The stimulation amplitude will be equivalent to 110% of the adjusted MT. Prior studies have safely utilized TMS with such design (VanDerwerker et al., 2018; Cristancho, Trapp, Siddiqi, Dixon, & Lenze, 2018). The seventh study visit will involve a 1-hour TMS/fMRI session while the participant is engaging in a behavioral task.. This visit is designed to examine brain and behavioral changes after the first round of neuromodulation. The seventh and the eighth visit will be scheduled at least one week apart. The eighth, ninth, and tenth study visits will mirror the fourth, fifth, and sixth study visits and will involve neuromodulation with either the optimized or least-optimized individual frequency. The order of optimized and least-optimized frequencies will be counterbalanced across participants between Visit 4-6 and Visit 8-10 (i.e., half of the participants will receive stimulations of the two frequencies in one order, and the other half will receive stimulations of the two frequencies in the reverse order). The

eleventh visit will mirror the seventh visit and will examine brain and behavioral changes after the second round of neuromodulation.

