
same interleaved pattern at the same stimulation site as the TMS/fMRI session but with either the optimized frequency determined from that session or the frequency least successful in moving their brain state (half of the participants will receive optimized stimulation frequency, and the other half of the participants will receive least-optimized stimulation frequency during these sessions). The present study utilizes the same FDA-approved devices (Magventure Cool-Coil B65, MagVenture X100 Stimulator) to administer TMS. The TMS system is housed in the Richards Biomedical Building. Only individuals trained by the Principal Investigator ([name].) and, [name] (M.D.) will dispense TMS. In addition to receiving TMS, participants will complete questionnaires and computerized tasks during these visits. The tasks will assess reaction time, working memory, decision-making. The decision-making task will be incentive-based and the amount the participant earns will be added to their final study compensation. During some of the tasks, we may ask subjects to wear a passive eye-tracking device to record the location of your gaze at any particular time. The order of tasks will be randomized for each participant. Visit 7 will involve a 1-hour TMS/fMRI session. Participants will complete the working memory N-back task while inside the scanner. The purpose of this visit is to examine the brain and behavioral changes after the first round of neuromodulation. Visit 8-10 will mirror Visit 4-6 and will involve neuromodulation with either the optimized or least-optimized individual frequency. The order of optimized and least-optimized frequencies will be counterbalanced across participants between Visit 4-6 and Visit 8-10 (i.e., half of the participants will receive stimulations of the two frequencies in one order, and the other half will receive stimulations of the two frequencies in the reverse order). Visit 7 and the Visit 8 will be scheduled at least one week apart. In addition, unless the MRI is unavailable or we encounter scheduling constraints, Visit #3-Visit #7 will be scheduled within the same work week, such as Visit #3 is on Monday, Visits #4-7 are Tuesday/ Wednesday/Thursday, respectively, and Visit #7 is on Friday. Similarly, Visit #8-Visit #10 will be scheduled 4 work-days in a row, either Monday-Thursday or Tuesday-Friday. Visit 11 will mirror Visit 7 and examine brain and behavioral changes after the second round of neuromodulation. Monitoring will include: (1) successful recruitment, retention; (2) subject adherence; (3) safety and tolerability.

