**Analysis Plan**

For the primary within-subjects analyses, a time (pre vs post rTMS) by condition (optimized vs least-optimized frequency) ANOVA will be done both on task performance as well as fMRI voxelwise brain responses.

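### Carryover between the two stimulation rounds is guarded against only by a minimum one-week gap, and the pooled ANOVA has no carryover-free estimate and no defined 'pre' value for round 2

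*Combined protocol and SAP*

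**What the plan says.** Each participant receives three days of stimulation at one frequency and later three days at the other. On order, the Design section says: "The order of optimized and least-optimized frequencies will be counterbalanced across participants between Visit 4-6 and Visit 8-10". Between rounds it requires only this: "The seventh and the eighth visit will be scheduled at least one week apart". The Procedures section repeats the rule ("Visit 7 and the Visit 8 will be scheduled at least one week apart"). Neither place calls the gap a washout, says how long effects are expected to last, or requires a return to baseline.

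The post-round scan is a separate visit. Of Visit 7, Design says: "This visit is designed to examine brain and behavioral changes after the first round of neuromodulation". Round 2 goes straight to stimulation ("The eighth, ninth, and tenth study visits will mirror the fourth, fifth, and sixth study visits"), and the schedule under Study duration lists no scan between Visit 7 and Visit 11.

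The Analysis Plan is one sentence: "a time (pre vs post rTMS) by condition (optimized vs least-optimized frequency) ANOVA will be done both on task performance", and likewise on voxelwise fMRI responses. It names no period, order or carryover term and no first-round analysis, and it does not define 'pre' for either round.

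**The concern.** The primary outcome is change measured at a visit after stimulation has ended, so the study relies on effects that outlast stimulation. The hypothesis is also that the optimal frequency has the larger effect. If what remains is proportional to the effect, it is unequal between conditions. Counterbalancing does not remove unequal carryover, and neither does a period term.

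At stake is how the main result is read. A null pooled contrast could mean that frequency makes no difference or that round 1 had not worn off. With a different choice of 'pre', the contrast could instead be inflated. The plan provides nothing that would help a reader judge which.

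**Working it through.** **Inputs.** Accrual gives at least 28 usable participants from up to 38 enrolled. Half per order makes 14 and 14. No alpha, power, effect size, SD or correlation is stated, so the figure of 28 cannot be reproduced. For illustration I assume a two-sided 5% test, one scalar outcome, a standardized within-person difference of 0.549 (the size that 28 participants detect with 80% power), and a correlation of 0.7 between visits. The persisting fraction c is also assumed.

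**Timing.** The usual week is given as "Visit #3 is on Monday, Visits #4-7 are Tuesday/ Wednesday/Thursday, respectively, and Visit #7 is on Friday", reading the middle item as Visits 4-6. The last round-1 stimulation is then on Thursday and Visit 7 on Friday. Procedures starts round 2 on a Monday or Tuesday, so with at least a week after that Friday the earliest Visit 8 is a Monday, 11 days after the last stimulation. If the fourth consecutive work-day is Visit 11, as seems intended, the round-2 outcome falls on Thursday, 14 days after it. So c is persistence at about two weeks, while Visit 7 needs persistence of about one day.

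**Bias.** Let O and L be the effects of the optimal and least-optimal rounds, and D = O - L.

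- *Pre-round-1 baseline shared by both rounds.* Optimal first: O - (L + cO). Least-optimal first: (O + cL) - L. The average is D(1 - c/2).
- *Visit 7 as the round-2 'pre'.* Optimal first: O - (L + cO - O). Least-optimal first: (O + cL - L) - L. The average is D(3 - c)/2.
- *Equal absolute carryover k, shared baseline.* The average of (D - k) and (D + k) is D, so it cancels.

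**Power with the shared baseline.** The noncentrality is 0.549 × (1 - c/2) × √28 on 27 df: 2.91, 2.76, 2.54 and 2.18 for the four rows.

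| c (assumed) | Shared baseline, contrast/D | Power, n = 28 | Visit 7 as 'pre', contrast/D |
|---|---|---|---|
| 0 | 1.000 | 80% | 1.500 |
| 0.10 | 0.950 | 76% | 1.450 |
| 0.25 | 0.875 | 69% | 1.375 |
| 0.50 | 0.750 | 56% | 1.250 |

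Simulation with 14 per order, a period shift and correlation 0.7 agreed: the pooled estimate was 1.00, 0.87 and 0.75 of D at c = 0, 0.25 and 0.50.

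**Period term.** If L is half of O and c = 0.50, simulated power is 49% without a period term and 55% with one. The term recovers precision, but the estimate stays at about 0.75D.

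**First-round estimate.** Comparing the orders at Visit 7, adjusted for the pre-round-1 value, involves no carryover between rounds. In simulation it stayed at 0.99 to 1.01 of D throughout. Its SE is √(1 - 0.7²) × √(1/14 + 1/14) = 0.714 × 0.378 = 0.27 SD (simulated 0.273), giving a 95% CI of about ±0.55 SD. The pooled SE is √(2 × 0.3)/√28 = 0.775/5.29 = 0.15 SD. The reference effect is 0.549 × 0.775 = 0.43 SD, smaller than the first-round half-width.

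**The case against.** The strongest reply is that nothing shows an effect lasting two weeks. That is right. A reader might infer from the short gap that carryover will occur, but the documents give no duration and support no value of c.

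A reader might also infer that carryover must shrink the contrast. That does not follow either. Shrinkage below D needs carryover that is larger after the stronger condition and a baseline shared by both rounds. With Visit 7 as 'pre', the contrast is above D for any c below 1.

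Behaviour may have a further option. Procedures says of Visits 4-6, which Visits 8-10 mirror: "In addition to receiving TMS, participants will complete questionnaires and computerized tasks during these visits". Working memory is among the tasks. A Visit 8 value taken before stimulation would leave the contrast unbiased if the residue did not decay by Visit 11, and slightly inflated if it did. But the plan does not say whether the tasks come before or after stimulation, or name them as 'pre', and there is no equivalent for the scan.

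The first-round estimate is also weak as a detector. With D = 0.43 SD, its 95% CI lies wholly above the pooled estimate in about 3% of simulated trials at c = 0.50 and 9% at c = 1. With no carryover at all, it still exceeds the pooled estimate by 0.2 SD in 19%. This rules out a rule triggered by a larger first-round estimate. It does not rule out reporting that estimate with its interval.

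**Conclusion.** The concern stands as an unexamined risk of bias whose direction the plan leaves open. A minimum gap is the only safeguard, both rounds enter one ANOVA, 'pre' is undefined for round 2, and no carryover-free estimate is planned.

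Under proportional carryover and a shared pre-round-1 baseline, the contrast is 5% to 25% too small for c from 0.10 to 0.50, and power drops from 80% to between 76% and 56%. Using Visit 7 as 'pre' makes it 45% to 25% too large over the same range, and 50% too large with no carryover at all. The power figures describe one scalar outcome, not voxelwise maps.

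It would be too strong to say that the data cannot yield a carryover-free estimate. The planned visits supply one, provided order is allocated at random. The documents say only that order is counterbalanced; the randomization they describe is of task order.

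**What to change.** Keep the crossover analysis as primary and add the following to the Analysis Plan before outcome data are examined:

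- State that one named pre-round-1 measurement is 'pre' for both rounds, and that Visit 7 is not the round-2 'pre'.
- Include a period term.
- State how order is allocated. If it is random, pre-specify as a sensitivity analysis the Visit 7 comparison of optimal with least-optimal between the two order groups, adjusted for the pre-round-1 value. Report it with its 95% CI beside the pooled estimate, for task performance and one named main brain measure.
- State that a null pooled result will not by itself be reported as evidence that the frequencies are equivalent, because carryover cannot be excluded.
- Do not use a carryover pre-test, or a comparison of the two estimates, to choose or relabel the primary analysis.

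The cost is plan wording and one further regression for each of the two outcomes, on data already to be collected. No visit or participant is added. The drawback is imprecision: with about 14 per order and a 95% CI of about ±0.55 SD (assumed correlation 0.7), the first-round estimate helps interpretation and cannot replace the primary test.
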